## **3 Investigational Plan**

Study Phase: Remote Recruitment

Study Group: All participants

Setting: Remote

Timing: Recruitment will occur within 6 months of ED visit, potential participants will complete baseline study components within 5 business days of screening eligible for study and agreeing to participate.

For patients that visited the LCH ED, eligibility for screening will be determined from reports generated from Epic. The invitation to complete the eligibility screening questionnaire will be distributed by email, text message, phone call, postcard, flyer in ED room, ED discharge summary paperwork, and MyChart Research Recruitment messages.

# Emergency Medicine Prospective Protocol

For patients that have not visited the LCH ED and are seeking care at LCH affiliated sites, we will not use EPIC. The only recruitment method used for the part 1 screening survey will be flyers hung in the patient treatment rooms at these sites. Patients will have the opportunity to scan the QR code or enter the survey link onto their phones or personal device to take the survey remotely. Once a family completes the screening survey, the RC will determine eligibility for part 2. All part 2 procedures will occur remotely between the parent and the RC.

For initial recruitment of study participants for the part 1 screening survey, we will be using 5 methods of remote recruitment techniques. The following techniques will be used:

- 1) POSTCARDS: The use of postcards mailed to the parents of children eligible for this study and who have not responded to our previous efforts to reach them via email, text message and/or phone. This would be a final attempt to reach them via a mailed postcard.
- 2) FLYER IN ED ROOMS AT LCH: The use of a one page flyer to be hung up within all patient emergency rooms at LCH as another method to recruit families utilizing the ED in real time. The flyer will have a QR code and screening survey link on it.
- 3) FLYERS IN PATIENT TREATMENT ROOMS AT LCH AFFILIATED SITES: The use of a one-page flyer to be hung up within patient treatment rooms at Lurie Children's affiliate EDs (e.g., Central DuPage, Northwest Community) and Lurie Children's Immediate Care Centers (Lincoln Park and Northbrook). They flyer will have a QR code and screening survey link on it.
- 4) ED DISCHARGE SUMMARY INVITATION: The use of adding an invitation to complete our research study within the ED discharge summary notes that every patient/family will get when they leave LCH. Approval has been obtained from the Department of Emergency Medicine to add a few sentences along with a QR code and survey link to the bottom of the ED discharge summary notes for all patients at LCH.
- 5) MyChart RESEARCH RECRUITMENT: The use of the platform MyChart Research Recruitment as another method of reaching out to the parents of children eligible for our research study and inviting them to participate via messages sent to them in the portal.

Potential participants who screen eligible from the screening survey, will complete the informed consent process for part 2. The consent documents will be emailed to participants and available via a link to a Qualtrics survey in which the participant can provide their electronic signature. Informed consent discussion will occur between the potential participant and the research coordinator by phone prior to distribution of the baseline survey. Study procedures will otherwise follow the flow outlined below.

**Study Phase:** Baseline Visit (study enrollment)

**Study Group:** All participants

**Setting:** Emergency Department at LCH or remote (via phone/text message/email)

**Timing:** Study procedures must be complete during ED visit or within 5 business days

- Data collected from medical chart in EPIC: Information that will be recorded from the medical record includes: MRN number, chief complaint, weight, name of child, date of birth, and age. We will also use the medical chart to make sure the child does not meet any of the exclusion criteria as specified in the protocol and study staff are able to approach the family. And Epic reports will be used to identify families who have utilized Lurie Children's ED in the 6-months prior to the current date for remote recruitment.

# Emergency Medicine Prospective Protocol

- If the family did not visit the LCH ED, then the RC will not use EPIC to record any information. The parent enrolled will provide the study with the necessary information in the screening survey.
- Screening survey: If a child's parent/legal guardian chooses to be screened for eligibility in the full study, they will complete a short survey (~10 min.) on a study iPad or remotely on their own personal device. The survey will ask about their safety behaviors for kids in and around cars. It will ask about how their child usually rides in cars too. They should answer all questions for the child that is getting care at Lurie Children's. All answers are private, meaning they will not be shared with anyone outside of the study team.
- Baseline survey: If the child's parent/legal guardian screens eligible for the full study and consents to participate, they will complete a (baseline) survey on an iPad or remotely on their own device. This will take about 15-20 minutes. The survey will have questions about their use of car seats, and thoughts on child safety in and around vehicles. If they cannot finish the survey in person, they will have 5 business days to do this survey over the phone with a staff member or on their own device.
- After they get done with the survey, they will be randomly assigned (like flipping a coin) to one of two groups. They cannot pick the group that they will be in. The groups are:
  - Group 1 (Control --Usual Care): A study team member will give them an informational handout --see section 9 of IRB app "supporting document" for the PDF called, "Study Handout"
  - Group 2 (TCBD Intervention): A study team member will give them an informational handout --see section 9 of IRB app "supporting document" for the PDF called, "Study Handout". They will also have about a 20-minute counseling session (in-person or over the phone) with a study team member. During this session, they will talk about how their child normally rides in their car, their goals for traveling safely with their child, and how they might reach these goals. To protect their privacy, we will do this session in a private place. We will give the parent/legal guardian the option to have other family members/friends with them in the ED be present during the counseling session or step out of the room during the session. Also, to make sure that we've recorded their answers correctly, we ask for their consent to audio tape this session. This recording will only be used for research and the audio tapes will not include info that someone could use to recognize them. They can give consent to audio tape within the informed consent.

We will also show participants randomized to the intervention group how to use the study's website called, the "Car Seat Compass" (about 10 minutes). This website will give them custom feedback based on their answers within the baseline survey. This website will give them answers to common questions about traveling with children.

Two test cases have been built out on the development website, so that the IRB is able to log in and review content that may be similar to two common occurrences we expect to see within the study. To view these test cases, please follow the instructions listed below:

Test case 1 (study ID 400): Parent (Mother) who has a 12 month old child, currently using a rear-facing car seat, but plans to prematurely transition their child to a forward-facing car seat within the next 6 months. We are recommending that the child stay rear-facing until at least 2 years of age.

1. Using google chrome, go to website: <http://[name].miserver.it.umich.edu>.
2. Log in with the email: [contact] and the password: TCBDstudy
3. Review content within website based on this parent's situation.

# Emergency Medicine Prospective Protocol

4. The home page illustrates a road map of child restraints and provides the family with a green light message since the family is currently using the recommended car seat (rear-facing car seat) for that child. However, because they are planning to transition their child to a forward-facing car seat in the next 6 months, they will be eligible for the study and receive additional information on this in the "just for me" tab of website.
5. The tab labeled "just for me" surfaces information based on that parent's specific responses to the baseline survey and goes into more detail about the recommended car seat for the child of the caregiver.

Test case 2 (Study ID 300): Parent (Father) who has a 6 year old child, currently using a seat belt to restrain child in vehicle. We are recommending that they child is restrained with a booster seat.

1. Using google chrome, go to website: <http://[name].miserver.it.umich.edu>.
2. Log in with the email: [contact] and the password: TCBDstudy
3. Review content within website based on this parent's situation
4. The home page illustrates a road map of child restraints and for this family, provides a caution (yellow light message) since the family is using a non-recommended child restraint for the child. You will see the booster seat is highlighted in green to illustrate the recommended restraint for this family.
5. The tab labeled "just for me" surfaces information based on that parent's specific responses to the baseline survey and goes into more detail about the recommended car seat for the child of the caregiver.

During the baseline visit or within 5 business days, both groups (control and intervention) will also:

- Fill out a form that'll be used to get in touch with them for future follow-up visits --**see section 9 of IRB app "supporting document" for a document called, "Study Locator Form"**
- Complete a Tiny Cargo check-in. During this check-in, a study staff member will view how their child normally rides within their car. If they cannot do this check-in in-person, they will have 5 business days to send us photos. These photos will show us a few different views of their child as they normally ride in their car.
- **\*\*See section 9 of IRB app, "supporting documents" for a document called, "TCBD text library and error messages" and refer to the sheet labeled, "Response to errors."** This document provides scripted responses that the RA will use when major misuse and/or errors are visible during the Tiny Cargo check-ins. The TCBD intervention messages are referred to as "Scripted MI response" while the control group's responses are referred to as "scripted control response."

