## ***3.2 Allocation to Interventional Group***

After completing the baseline survey, all caregivers will be randomized into one of two groups: 1) TCBD intervention group, or 2) control group. Computerized, block randomization (block sizes from four to eight) will be applied to assign eligible caregivers to the TCBD intervention or control group in a 3:1 ratio. Blocks will be stratified by age groups related to child passenger safety recommendations (<2 years – rear-facing CRS, 2-4 years – forward-facing CRS, 5-10 years – booster seat) and the child passenger safety behavior that led to eligibility for study (not using the recommended restraint currently or planning a premature transition in the coming 6 months).

After the 6-month follow-up assessment, caregivers in the intervention group only who continue suboptimal CRS use will be re-randomized by computer in a 1:1 ratio to receive either the basic or enhanced intervention. The enhanced TCBD will include one additional motivational interviewing (MI) session by phone in Month 7/8 and one to two additional tailored text messages in Months 7-12 (total of 7 tailored tips during these months compared to 4 tailored tips for those in the basic TCBD). The extra text messages will be sent to those in the enhanced TCBD group until size-appropriate restraint use is observed. Caregivers receiving enhanced TCBD will be encouraged to obtain a free seat check with a certified child passenger safety technician (CPST) in the community. The primary outcomes (size-appropriate CRS use and CPaSS) will be assessed in-person at Months 6 and 12. The secondary outcome, the CPaSS trajectory, is a measure of correct and consistent restraint use in response to the intervention and will be assessed by scoring photographs submitted by caregivers (Months 1-5; 7-11).

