## **STUDY GROUPS:**

After participants complete the baseline survey, they will be randomized to either the control group (usual ED care with discharge instructions relevant to the child's diagnosis and a study handout) or the TCBD intervention group (an ED counseling session plus eHealth after ED discharge). Please also refer to section 3. D.1. for a complete outline of the study details for each group over the course of the study.

Main differences between intervention and control include the following:

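### The baseline CPaSS can be collected after randomisation and counselling, yet Section 6.2 does not limit the baseline covariate to pre-randomisation values; the likely attenuation of the 12-month CPaSS effect is small (minor)

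*Combined protocol and SAP*

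**What the plan says.** **Trigger for randomisation.** Section 3 (Investigational Plan), Baseline Visit, ties allocation to the survey: "After they get done with the survey, they will be randomly assigned (like flipping a coin) to one of two groups". Section 3.2 agrees ("After completing the baseline survey, all caregivers will be randomized into one of two groups"), and so does the Study Groups text ("After participants complete the baseline survey, they will be randomized to either the control group"). None of the three makes allocation wait for the check-in.

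**What comes next.** For the TCBD arm, the Baseline Visit text continues with "They will also have about a 20-minute counseling session (in-person or over the phone) with a study team member" and a demonstration of the website. Only then does it say "During the baseline visit or within 5 business days, both groups (control and intervention) will also" complete a locator form and a Tiny Cargo check-in. For that check-in, "If they cannot do this check-in in-person, they will have 5 business days to send us photos". On feedback, it says "This document provides scripted responses that the RA will use when major misuse and/or errors are visible during the Tiny Cargo check-ins"; the TCBD messages are a motivational-interviewing script, "while the control group's responses are referred to as" a separate control script.

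**The other order.** Section 5.1.1 lists survey, check-in, randomisation and counselling in that sequence. It also lets caregivers finish any of these remotely within 5 business days of enrolment.

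**Baseline score.** Section 5.1.1 has CPaSS recorded at the check-in. Table 1 in Section 3.3 schedules directly observed CPaSS at Months 6 and 12 only; remote CPaSS alone has a baseline time point.

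**Analysis.** Section 6.2, Aim 1, describes a model equivalent to ANCOVA. It adjusts for a baseline measurement when a single follow-up such as Month 12 is analysed, and at the first follow-up only in joint models. It sets no rule on when that measurement must have been taken. Other covariates enter only if a balance test is significant.

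**The concern.** ANCOVA on a baseline value estimates the treatment effect properly because randomisation makes that value independent of arm. A covariate measured after counselling loses this protection. If counselling has already raised the TCBD group's score, adjusting for it removes part of the effect under study, so the 12-month CPaSS estimate drifts toward zero. CPaSS is one of the two primary outcomes, and some of its components (fit, misuse, seating position) could change without a new seat. Only a difference between arms matters, because both arms get the same handout.

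**Working it through.** **Inputs from the documents.** Section 6.1: 204 control and 516 TCBD caregivers analysable; 75% of TCBD re-randomised at Month 6; detectable CPaSS difference 0.25 SD for basic TCBD v control. Section 3.2: re-randomisation 1:1. Section 6.2: two-sided 0.05.

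**Inputs not in the documents, therefore assumed.** ρ, the within-arm correlation of baseline and 12-month CPaSS (0.3 to 0.7); f, the share of check-ins made after counselling; d, the early between-arm shift in the score those check-ins record, in SD units. Section 6.1 itself says there is no basis for estimating the score's variability.

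**Step 1: the plan's own figure.** Basic TCBD = 516 × (0.25 + 0.75/2) = 322.5. The unadjusted SE is √(1/322.5 + 1/204) = 0.0895, and 0.25/0.0895 − 1.96 = 0.83, giving 79.8% power. This matches the stated 80%. The sample size therefore rests on an unadjusted comparison and does not use baseline adjustment.

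**Step 2: all TCBD v control, no contamination.** Unadjusted SE = √(1/516 + 1/204) = 0.0827; 0.25/0.0827 − 1.96 = 1.06, power 86%. With a clean baseline and ρ = 0.5, SE = 0.0827 × √(1 − 0.25) = 0.0716; 0.25/0.0716 − 1.96 = 1.53, power 94%.

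**Step 3: with late check-ins.** Expected estimate = 0.25 − ρ·f·d, with SE as for the clean baseline. At ρ = 0.5:

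| Share late f | Shift d | Bias ρ·f·d | Estimate (SD) | Power |
|---|---|---|---|---|
| 0 or any | any or 0 | 0 | 0.250 | 94% |
| 0.25 | 0.05 | 0.006 | 0.244 | 93% |
| 0.50 | 0.05 | 0.0125 | 0.238 | 91% |
| 0.50 | 0.10 | 0.025 | 0.225 | 88% |
| 1.00 | 0.10 | 0.050 | 0.200 | 80% |

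For half late with shift 0.10, power is 85% at ρ = 0.3 (clean 89%) and 95% at ρ = 0.7 (clean 99%). Section 3.2 states 3:1 allocation, whereas 516:204 is 2.53:1. At 540 v 180 and ρ = 0.5 the pattern is the same: unadjusted 83%, clean 92%, half late with shift 0.10 86%.

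**Step 4: break-even.** The contaminated adjusted test falls below the unadjusted one only if f·d exceeds 0.25 × (1 − √(1 − ρ²))/ρ. That is 0.038, 0.067 and 0.102 SD at ρ = 0.3, 0.5 and 0.7. Half late with shift 0.10 gives f·d = 0.05, below break-even at 0.5 and 0.7 and above it at 0.3.

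**Step 5: why basic v control is left out.** The basic group in Section 6.1 is all Month-6 responders (0.25 × 516 = 129) plus half of the non-responders (193.5). Responders are thus 129/322.5 = 40% of the group, against 25% of the arm. A null simulation of the unweighted comparison, with a clean baseline and response taken as the top quarter of a Month-6 score, gave about +0.06 SD and about 12% rejection at an assumed Month-6/12 correlation of 0.5. At 0.7 it gave about +0.11 SD and 30%. That selection bias runs opposite to the attenuation.

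**The case against.** **The order may be sound in practice.** Section 5.1.1 is the dedicated procedures section and puts the check-in first. But it lets any element slip, and three other places make the survey the trigger, so no order is enforced.

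**In-person check-ins are largely protected.** Section 8.2 describes observing the child in the vehicle used to reach the ED. Counselling there cannot change which seat came in that car. This stands, and it confines the exposure mainly to photo check-ins. It does not remove it, because Section 4.3 notes that study tasks have gone fully remote.

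**Late does not mean after counselling.** The 5 business days run from agreement to participate or from enrolment, not from randomisation, and phone counselling shares the window. A reader might infer that every deferred check-in follows counselling; the documents do not say so, and the share is unknown.

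**The arm-specific scripts prove less than they seem to.** They show that the arm is known when feedback is given. Feedback follows the observation, so it cannot contaminate that same observation.

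**The covariate is not really undefined.** In an ANCOVA the natural reading is the baseline value of the outcome. This is accepted; what is missing is the timing rule.

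**The loss is small.** In the quarter-late to half-late cases at correlation 0.5, the adjusted test still beats the unadjusted one. This also stands, and it is why the point is minor.

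**Conclusion.** The plan permits a post-counselling CPaSS to serve as the baseline covariate in the single-follow-up 12-month analysis. The consequence for all TCBD v control is an attenuation of 0.006 to 0.025 SD across the moderate cases at an assumed correlation of 0.5, with power of 93% to 88%. It is zero if no check-in is late or if counselling moves nothing within days. Severity: minor.

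Four stronger readings are not supported:

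- That the trial is underpowered or wrongly sized: Section 6.1 does not rely on baseline adjustment.
- That the effect could be halved: an estimate of 0.125 SD (about 42% power) at correlation 0.5 needs every check-in late and the whole 0.25 SD effect present within days.
- That basic v control is likewise biased toward zero: its Month-6 selection can push the other way and be larger.
- That restraint use is equally affected: it is exposed only if the check-in, rather than the pre-randomisation survey, supplies its baseline.

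In joint models only the first follow-up is baseline-adjusted, which narrows the exposure there.

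**What to change.** 1. **Reconcile the order.** Section 3 (Baseline Visit), Section 3.2, the Study Groups text and Section 5.1.1 should agree on whether the check-in precedes allocation, within the window that must also hold counselling.

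2. **Limit the covariate in Section 6.2 to values dated before randomisation.** For restraint use, take survey-reported restraint. For CPaSS, take survey-reported restraint plus the check-in CPaSS if it predates randomisation; otherwise enter a constant with a missing-baseline indicator. The indicator is fixed at allocation, so it cannot depend on arm, and everyone stays in the intention-to-treat analysis. Record check-in and randomisation date-times, and add a sensitivity analysis with the survey covariate only.

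   The cost is wording, two date-time fields and some power. In simulation for all TCBD v control (correlation 0.5; survey–CPaSS latent correlation assumed 0.3 to 0.6), power was 92% with a quarter lacking a pre-randomisation CPaSS, 90% with half and 86–88% with all, against 94% clean: about 2 to 8 points. If the survey goes on triggering randomisation, expect the lower end. Against the unfixed model with the same survey covariate, the fix was about 1 point lower at a quarter late with shift 0.05 and about 2 points higher at half late with shift 0.10. At the small end it buys an unbiased estimate, not power.

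3. **Separately, always include the Section 3.2 stratification factors** (age group and eligibility behaviour) as covariates, rather than adjusting only after a significant balance test. This costs nothing. The precision gain is small, and its size depends on assumed stratum rates.

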# Emergency Medicine Prospective Protocol

**Study Phase:** Monthly Photo Requests (During Months 1-5 and Months 7-11)

**Study Group:** All participants

**Setting:** Remote (text message via caregiver's mobile device)

**Timing:** Study procedures must be complete within each month (within 4 weeks)

## Monthly photo requests:

- **\*\*See section 9 of IRB app, "supporting documents" for a document called, "Tips & tricks for taking your monthly photo"** --this document will be provided to all participants enrolled in part 2 of the study. The RA will review this document during the ED baseline visit with the participant.
- No matter which group caregivers are assigned into at the baseline visit, we will contact the study participant again starting in 1 month. A member of our study team will send them a photo request via text message. This text message will ask them to share photos of their child as they normally ride in their car.
- These photo requests will be sent to their best phone number. All photos of their child will be sent back to us by the parent/legal guardian.
- They will get requests to submit photos a total of 8 times while taking part in this study (over the next 12 months). We will be asked for these photos during months 1- 5, and Months 7-11 of the study.
- They will get these photo requests only on the days and during the times that they tell us they are able to get messages from us. To update the days and times that they are free to be contacted, caregivers can reach out to our team at by phone or email or text message
- The participant will have a 4 hour window of time to submit their photo requests each month with an additional 4 hour grace period. If a participant submits their photos during their window of time each month and the photos meet the necessary requirements (meaning the RA is able to visibly see all elements of the child sitting in the car seat, then the photos will be approved and the participant will earn \$5 that month. Participants can earn a total of \$40 if they complete all 8 photo requests during their specified window each month and the photos are approved. If the participant completes 4 months of photo submissions in a row, then they will hit a "streak" and will earn an additional \$5. They can hit a "streak" up to 2 times over the course of the study, so they can earn up to an additional \$10.
- Photo message response time (evaluate and response) from study staff will be 24-48 hours. Photo requests will not be sent if the staff are not available to respond during that time window.
- For study data collection purposes, after the research team receives photos back from the study participant, the research team will use the Child Passenger Safety Score (CPaSS) to access for correct use of the child's restraint system. See below for a document called "CPaSS data elements for IRB submission" to view the tool that will be used to access for visible errors/misuse that may be seen by the study team.
- If major misuse or errors are visible within a participant's photo submissions, they will receive a scripted text message from the study team within 24-48 hours after the photo is submitted. Participants in the TCBD intervention group will receive messages in the spirit of Motivational Interviewing style while the control group will receive similar messages without the spirit of MI.
- **\*\*See section 9 of IRB app, "supporting documents" for a document called, "TCBD text library and error messages" and refer to the sheet labeled, "Response to errors."** This document provides scripted text messages that the RA will use when major misuse and/or errors are visible within the photo submissions each month. The TCBD intervention messages are referred to as "MI spirit text messages" while the control group's text messages are referred to as "control text messages."

